## 5.2. Baseline Definition

The protocol specifies Day 0 as baseline, but the Clinical Data Interchange Standards Consortium (CDISC) standard refers to the baseline as Day 1; therefore, baseline date will be referenced as Day 1 in this document. Further information on the definition of study and SLE medication phases is presented in Section 9.5.2.

In general, the baseline value of a variable will be defined as the value of the variable measured at the enrollment visit per eCRF . The exceptions are:

- i. For SLICC, and SLEDAI 2000, measurements done within  $\pm 30$  days of enrollment day will be considered as baseline. If there are multiple records that meet this criteria for the same measurement, the worst-case value will be selected as the baseline value. If the values are equal, the measurement which takes place first will be selected as the baseline value.
- ii. For laboratory, measurements done within  $\pm 30$  days of enrollment day will be considered as baseline. If there are multiple records that meet this criteria for the same measurement, the measurement which takes place first will be selected as the baseline value.
- iii. For SLE medications, a 3-day post enrollment rule is applied such that SLE medications started or initiated between study days 1-4 of enrollment (i.e. Study Day 1, 2, 3 or 4) are counted as baseline medication.
- iv. All hospitalizations (SLE-related and non-SLE-related) which occurred (based on admission date) within 6 months prior to or on the enrollment visit date.

**5.3. Visit/Assessment Time Window and Descriptor**

Follow-up assessments are expected to be performed every six months  $\pm 2$ -month time window. Analysis visit will be created for mapping data assessments into correct visit time point. This variable will be used in all analyses that require a visit number, regardless of the collected visit in the eCRF. If there are multiple visits done within a expected visit time window, the visit with the worst-case value will be used. Further details are provided in Section 9.5.1.

Study Period	Analysis Visit Number (AVISITN)	Target Visit Time	Expected Visit Interval	Expected Assessment Interval (Days) 	Target Study Day (for events slotting) 	Table/Graph Descriptor (Months)
Enrollment	1	Day 1		$\leq 91$ days		
Baseline	1.5					
Follow-up	2	6 Months	4 to 8 Months	92 – 274 	183	6
	3	12 Months	10 to 14 Months	275 – 456	366	12
	4	18 Months	16 to 20 Months	457 – 639	548	18
	5	24 Months	22 to 26 Months	640 – 822	731	24
	6	30 Months	28 to 32 Months	823 – 1004	914	30
	7	36 Months	34 to 38 Months	1005 – 1187	1096	36
	8	42 Months	40 to 44 Months	1188 – 1369	1279	42
	9	48 Months	46 to 50 Months	1370 – 1552	1461	48
	10	54 Months	52 to 56 Months	1553 – 1735	1644	54

	11	60 Months	58 to 63 Months 	1736 – 1918	1827	60
--	----	-----------	------------------------------	-------------	------	----

Expected study day interval for mapping data assessments date to visit. Lower limit = Target Study Day-91 (i.e. approximately 3 months). Upper limit = Lower limit of next interval-1, 60 months upper limit is calculated as Target Study Day+91.

Target study day for slotting events (e.g. AESI and Hospitalization) to time point. Target day is calculated as  $365.25/12 * \text{xx months}$  rounding up to the nearest integer.

Expected assessment days for 6 months visit for all clinical data except for AEs and Hospitalizations (which collection should start from Day 1 for AEs and Day 2 for hospitalizations and then slotted using the target study day), and SLE medications (which starts from Day 5).

Visits and events collected after 63 months will not be summarised or analysed.

All new cases of AESIs, medications, and/or hospitalizations occurring since the last visit assessment will be collected. The analysis time point will be assigned using the target study day and will be used for all corresponding statistical analysis and data summary. The study day will be assigned based on the date of event, measurement, or assessment, if present. Else, study day will be assigned based on the date of the visit.

#### 5.4. Subjects' Study Status

A “study completer” is defined as a subject who did not withdraw from the study, was not lost to follow-up or not deceased prior to the 5-year follow-up. Study subject's completion status will be presented and described as ‘Completed’ or ‘Withdrawn’. ‘Ongoing’ status will remain for the final analysis dry-run. At that time, subjects with ‘Ongoing’ status will be further grouped by time since last contact date as at the data cut date. This will be categorized as: 0.5 year, 0.5 - < 1 year, 1 - < 2 years, 2 - < 3 years, < 4 years, 4+ years (see Section 9.5.3). For subjects who withdraw, the following reason for withdrawal will be reported as captured on the eCRF: adverse event including death, lost to follow-up, withdrew consent, investigator discretion and site closed/terminated. Subjects who were still ongoing as of last interim analysis will be considered lost to follow-up (LTFU) only at the final 60-month visit following completion of 5-years + 3 months since enrollment into the study. The last contact date (as defined in Section 9.5.3) will be taken as the date of LTFU.

#### 5.5. Multicentre Studies

In this multicentre global study, enrollment will be presented by country and site. For subjects who switched study sites, the last site where study was completed will be reported. Study sites will be grouped into three regions (US/Canada vs Europe vs Other).

#### 5.6. Examination of Covariates, Other Strata and Subgroups

##### 5.6.1. Covariates and Other Strata

The list of potential confounding factors included in statistical analysis to minimize selection and confounding bias will be listed in Appendix 9.9.

Descriptive summary will be performed for the subject demographic characteristics and some other covariates:

- i. Baseline SDI (0 vs  $\geq 1$ )
- ii. Hospitalization within 6 months prior to study enrollment (Yes vs No)
- iii. SLEDAI 2000 score at baseline ( $<10$  vs  $\geq 10$ )
- iv. Baseline Immunosuppressant use (Yes vs No; mycophenolate vs immunosuppressant other than mycophenolate)
- v. Duration of prior/baseline medication (i.e. Immunosuppressants, anti-malarials or other) ( $<1$ , 1-2 or  $>2$ years)
- vi. SLE diagnosis duration ( $<1$ , 1- $<5$ , 5- $<10$ , 10- $<15$ , 15- $<20$   $\geq 20$ years)
- vii. Oral corticosteroids dose (mg/day) use at baseline (Always  $<7.5$ mg/day,  $\geq 7.5$ mg/day for  $\leq 2$  weeks or  $\geq 7.5$ mg/day for  $> 2$  weeks)
- viii. Region (US/Canada vs Europe vs Other)
- ix. Race (Black, White, Asian, Other)
- x. Positive anti-dsDNA at baseline
- xi. Low complement at baseline

For the elderly population, sub-group summary will be performed as part of the end of study reporting (to fulfil the Elderly analysis post-approval commitment). Any analysis for elderly sub-group will be restricted to subjects aged 65 yrs and older, grouped as  $\geq 65$  years and age  $\geq 75$  years if feasible.

### 5.6.2. Examination of Subgroups

Descriptive summaries and statistical analyses will be performed separately for the two study cohorts (Current Users and Treatment Initiators).

Study Cohort	Definition / Criteria
Current Users	
 
• Subjects who have received or started qualifying medication(s) for <math>\geq 2</math> months (<math>\geq 62</math> days) prior to enrollment (Day 1)
 

Treatment Initiators	
 
• Subjects who have initiated or started qualifying medication(s) in the last 2 months (<math>< 62</math> days) prior to enrollment into the study (i.e Baseline SLE medication initiation <math>< 62</math> days from study Day 1)
 

*Study cohort can be determined for 'Eligible' subjects only (see section 4)*

For the purpose of study cohort assignment to either a current user or a treatment initiator, the following rules will be used to determine when a subject first received Benlysta and/or Non-Benlysta SLE medications:

- For BENLYSTA subjects: this will be the start date of earliest baseline Benlysta medication.

- For NON-BENLYSTA subjects: this will be the start date of study-qualifying non-benlysta SLE medications or the most recently added immunosuppressant if they are on multiple medications at baseline.

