5.2 Exclusion Criteria

Patients will be excluded from participating in the registry if they meet any of the following exclusion criteria:

1. Treatment with an investigational drug within one year of enrollment. Investigational drug applies to any drug not approved for sale in the country it is being used.
2. Currently enrolled in a placebo-controlled BENLYSTA (belimumab) clinical trial or a continuation protocol where belimumab is used as an investigational agent.
3. Patients who have a history of BENLYSTA exposure, but are not currently receiving BENLYSTA.
4. Patients only receiving an anti-malarial for SLE.
5. Patients only receiving steroids for SLE.

6 Data Collection

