6.1 Study Enrollment Evaluations

The following data will be collected at enrollment (baseline). Data collection for enrollment may be carried out over more than one clinical evaluation visit.

1. Written informed consent (including consent for the use and disclosure of research-related health information).
2. Demographics (eg, age, gender, race/ethnicity (where allowed by local regulation), smoking history, alcohol use)
3. Medical history (including SLE history). Note: To collect additional important information on potential suicidality-related events, should any of the psychiatric events marked with an asterisk in [Appendix 2](#) be present at enrollment, the investigator should complete the Possible Suicidality-Related History Questionnaire (PSRHQ) eCRF (see [Appendix 3](#)).
4. Potential Confounders for Malignancies and/or Infections List (refer to [Appendix 7](#)).
5. Obtain historical and current SLE medications (immunosuppressants, antimalarials, corticosteroids and biologics). The name of the each SLE medication and start and stop dates will be recorded. In addition, for corticosteroids, the prescribed dose will be recorded. If the patient is receiving BENLYSTA, the date of first dose, and route of administration (IV or SC) will be recorded as well as name of the other SLE medications the patient was receiving at the time BENLYSTA therapy was initiated.
6. SLEDAI 2000 (see [Appendix 6](#)). To complete SLEDAI 2000, data from the following laboratory tests if available: Hematology (WBC, platelets), complement (C3, C4), anti-dsDNA, routine urinalysis, and spot urine for macroscopic/microscopic/proteinuria assessments. Note: Laboratory values should not be attributed on the SLEDAI 2000 unless laboratory values were obtained within 30 days of enrollment otherwise the laboratory values will be noted as not done.
7. SLICC/ACR Damage Index ([Appendix 5](#)).
8. Hospitalizations occurring in the previous 6 months.

9. Confirm patient meets study eligibility criteria.

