### 9.5.2. Study and Concomitant Medication Phases

Study Phase	Definition
Historical	Date < Enrollment Date
Baseline	Enrollment Date
Follow-up	Date > Enrollment Date

Medication Phase	Definition	
Historical	Medications stopped prior to enrollment date (Day 1). For BENLYSTA only:  With regards to interruptions (i.e. stopping & restarting the medication), medications that stop within the 98 days window before enrollment, and don't restart within 98 days of the medication end date, will be classified as historical.	Medication End Date < Study Enrollment Date, excluding interruptions in medications for BENLYSTA only (as defined in the baseline medication phase)
Baseline	Medications started on or prior to enrollment date (Day 1) and still ongoing at or after enrollment, or for BENLYSTA only: Benlysta that stops within 98 days before enrollment and restarts, such that restart date – stop date ≤98 days and subsequent Benlysta end date is ongoing or after enrollment date. Such cases are considered interruptions, the medication is classified as baseline.	Medication Start Date ≤ Enrollment Date* ≤ Medication End Date, or accounting for interruptions for BENLYSTA only: Enrollment Date -98 ≤ Medication(A) End Date < Enrollment Date* and Subsequent Medication(B) Start Date ≤ Medication(A) End Date + 98 and ((Subsequent Medication(B) End date ≥ Enrollment Date) or (Subsequent Medication(B) End Date is missing))
Post-Baseline	Medication is still ongoing after enrollment day or medications end date is after enrollment.	Medication End Date is missing or Medication End Date > Enrollment Date

\* Consider SLE medication(s) started within 3 days following the enrollment date (i.e Medication started or initiated at Day 1, 2, 3, or 4) as Baseline Medication (i.e Enrollment Date ≤ Medication Start Date ≤ Enrollment Date +3)

Study Day

 
Calculated as the number of days from Enrollment Date (Day 1):                             
 
Ref Date = Missing → Study Day = Missing
 
Ref Date < Enrollment Date → Study Day = Ref Date – Enrollment Date
 
Ref Date ≥ Enrollment Date → Study Day = Ref Date – (Enrollment Date) + 1
 
 
 

For all parameters, changes from baseline will be derived as follows:

Definition	Reporting Details
Change from Baseline	= FU Visit Value – Baseline Value
% Change from Baseline	= 100 x [(FU Visit Value – Baseline Value) / Baseline Value]

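### SAP 5.6.2 and 9.5.2 together class some long-term BENLYSTA users with a gap of 38 to 98 days as Treatment Initiators, depending only on how long before enrollment the gap fell

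*SAP*

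**What the plan says.** SAP 5.6.2 splits subjects into Current Users and Treatment Initiators at 62 days; an initiator has "Baseline SLE medication initiation < 62 days from study Day 1". It introduces the dating rule with "the following rules will be used to determine when a subject first received Benlysta and/or Non-Benlysta SLE medications". For the BENLYSTA group the rule is "For BENLYSTA subjects: this will be the start date of earliest baseline Benlysta medication".

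Baseline is a defined phase in SAP 9.5.2. A course that ended before enrollment is normally historical. There is one exception, for BENLYSTA only: "Benlysta that stops within 98 days before enrollment and restarts", with no more than 98 days between stop and restart and the later course still running at enrollment. Of these the SAP says: "Such cases are considered interruptions, the medication is classified as baseline". Courses that stop in that window but "don't restart within 98 days of the medication end date, will be classified as historical".

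The protocol lets restarters in. Exclusion 3 (Protocol 5.2) removes only "Patients who have a history of BENLYSTA exposure, but are not currently receiving BENLYSTA". Protocol 6.1 collects start and stop dates of historical and current SLE medications, and adds: "If the patient is receiving BENLYSTA, the date of first dose, and route of administration (IV or SC) will be recorded".

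**The concern.** The rule is announced as finding first receipt of BENLYSTA, but it cannot see any course that 9.5.2 calls historical. A subject who restarted shortly before entry can therefore be filed as an initiator after earlier, possibly long, use.

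The interruption rule does not fully prevent this, because it carries two conditions. One is the length of the gap, which is relevant to continuity of treatment. The other is how close the earlier stop lies to enrollment, which is not. Two subjects with the same gap can land in different cohorts.

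What is at stake is the content of the BENLYSTA initiator AESI displays: Tables 24.112, 24.122, 24.212, 24.312 and 24.412, and the time-period summaries 23.020 and 23.120. The additional safety comparison of BENLYSTA initiators in Protocol 8.3.2 would inherit the same classification if it used this derivation. No later step corrects the mix: the covariate list in SAP 9.9 has no term for prior BENLYSTA, and the weighted tables (54.010, 54.020) are not split by cohort.

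**Working it through.** The plan states no figure that depends on this rule, so the check is to apply the rule to dated cases.

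**Inputs.** Initiator cut-off: under 62 days before Day 1 (SAP 5.6.2). Interruption rule: earlier stop no more than 98 days before enrollment, and restart no more than 98 days after that stop (SAP 9.5.2). A start up to 3 days after enrollment still counts as baseline (SAP 5.2, 9.5.2). Each case has an earlier course that began long before enrollment and a restart that is ongoing.

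| Earlier course ends | Restart | Gap (days) | Earlier course is | Cohort |
|---|---|---|---|---|
| Day -30 | Day -10 | 20 | baseline | Current User |
| Day -98 | Day -61 | 37 | baseline | Current User |
| Day -99 | Day -61 | 38 | historical | Initiator |
| Day -90 | Day -20 | 70 | baseline | Current User |
| Day -110 | Day -40 | 70 | historical | Initiator |
| Day -365 | Day -30 | 335 | historical | Initiator |
| Day -130 | Day -90 | 40 | historical | Current User (restart itself is over 62 days back) |

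**Limits of the affected band.** Let the earlier course stop *s* days and the restart occur *r* days before enrollment, with gap *g* = *s* − *r*. A subject with a gap of 98 days or less becomes an initiator when *r* ≤ 61, *s* ≥ 99 and *g* ≤ 98.

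- Shortest gap: 99 − 61 = 38 days.
- Earliest stop: 61 + 98 = 159 days before enrollment; latest stop: 99 days before.
- For a given gap, the restart dates that produce an initiator run from 99 − *g* to 61 days before enrollment, which is *g* − 37 dates. Restarts can fall on 65 dates (61 before, the day itself, 3 after). So 1 of 65 dates is caught at a 38-day gap, 33 of 65 at 70 days and 61 of 65 at 98 days.

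These are counts of calendar positions, not of patients.

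**Result by gap, for restarts less than 62 days before Day 1.** At 37 days or less: always Current User. At 38 to 98 days: either, according to when the earlier course ended. At 99 days or more: always Initiator.

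**Effect on a rate.** If a share *f* of the initiator group are restarters whose AESI rate is *k* times that of new users, the group rate is the new-user rate times 1 − *f*(1 − *k*). Neither *f* nor *k* is in the documents. Assuming *f* of 5% to 20% and *k* of 0.5 to 0.75, the rate is lowered by 0.05 × 0.25 = 1.25% up to 0.20 × 0.5 = 10%. If *k* exceeds 1, the sign reverses.

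**The case against.** Several points on the other side are sound.

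A reader might infer that every previously treated restarter becomes an initiator. The documents do not support that: gaps of 37 days or less, and any restart 62 or more days before Day 1, give a Current User.

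A reader might also take every restart after a gap over 98 days as an error. The protocol's definition of initiator never requires that the patient be new to BENLYSTA, and 98 days is the 14-week window it describes as about five half-lives. Treating such a restart as a new course is a defensible washout definition. The comparison group is not treatment-naive either, since SAP 5.6.2 uses the most recently added immunosuppressant. Moving all restarters to Current Users would create its own mislabelling, for example of someone five days into a new course years after a short one. What remains for long gaps is that the stated purpose, first receipt, is not what the rule delivers.

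A third tempting reading is that initiator rates are biased downward. That rests on an assumed *k* below 1. Protocol 1.1 itself raises cumulative immunosuppressant exposure as a possible contributor to malignancy, so the direction may differ by AESI. Random error is also large. With the Table 8-1 rates and the full planned 7,773 BENLYSTA patient-years, the approximate relative 95% half-width, 1.96/√events, is 9% for serious infection (7,773 × 0.0580 ≈ 451 events), 27% for deaths (≈ 53) and 47% for malignancy excluding NMSC (≈ 18). The initiator subset will be less precise.

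The case report form is not shown, and the date of first dose in Protocol 6.1 may mean first ever or first of the current course. It cannot be said that the SAP ignores a known first-ever date. However, SAP 9.5.2 is written for separate earlier and later records, so restarts recorded as two courses are expected.

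Finally, the switching footnote in SAP 5.1, which does not count a gap of 98 days or less as leaving BENLYSTA, formally governs follow-up rather than the period before entry. It is supporting evidence only. The inconsistency stands on 5.6.2 and 9.5.2 alone.

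**Conclusion.** The point holds in a limited form. BENLYSTA subjects who restarted less than 62 days before Day 1, and whose earlier course falls outside the interruption rule, are classed as Treatment Initiators under a rule said to date first receipt. For gaps of 38 to 98 days, with the earlier stop between Day -159 and Day -99, this is an internal inconsistency, because an identical gap nearer enrollment gives a Current User. For longer gaps it is a mismatch of wording with a reasonable definition.

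The conclusion assumes that 9.5.2 is programmed as written and that stopped and restarted courses are held as separate records. The number of subjects affected and the direction of any bias cannot be determined from the documents. The overall and weighted BENLYSTA versus NON-BENLYSTA rates do not use this classification and are unaffected. The change is worth making because the defect is certain where it applies and cheap to remove, not because a large bias has been shown.

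**What to change.** 1. In SAP 5.6.2, for cohort assignment only, chain back from the BENLYSTA course current at enrollment through all BENLYSTA records separated by gaps of 98 days or less, whatever their distance from enrollment. Use the start of that chain. The baseline phase in 9.5.2 can stay as it is for its other uses.
2. Replace the reference to when BENLYSTA was first received with the start of the current course, so that a restart after more than 98 days is openly a new course.
3. Report the number of such restarters by cohort in Table 1.000.
4. Add a sensitivity run of the BENLYSTA initiator AESI rates (Tables 24.112, 24.122, 24.212, 24.312, 24.412) that excludes anyone with an earlier historical BENLYSTA record.

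The start and stop dates needed are already collected under Protocol 6.1. The cost is a somewhat smaller BENLYSTA initiator group, with slightly wider intervals, and a little extra programming.

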## 5.7. Multiple Comparisons and Multiplicity

No adjustments for multiple comparisons are planned. There will be no formal statistical testing, analyses including comparison of estimates will be descriptive only..

## 5.8. Other Considerations for Data Analyses and Data Handling Conventions

Other considerations for data summaries, analyses and data handling conventions are outlined in the following appendices:

Section	Component
9.2	Appendix 2: Exposure Strategy, Analysis Approach and Individual's Subject-Years Calculation
9.3	Appendix 4 Appendix 3: Review and Categorization of Adverse Events of Special Interest
9.4	Appendix 4: Data Display Standards & Handling Conventions
9.5	Appendix 5: Derived and Transformed Data
9.6	Appendix 6: Reporting Standards for Missing Data
9.7	Appendix 7: Laboratory Tests

## 6. STUDY POPULATION ANALYSES

### 6.1. Overview of Planned Study Population Analyses

Study population analyses will be based on the 'Eligible' population. These analyses will include descriptive summaries of subject's disposition, demographic and baseline characteristics, SLE concomitant medications, historical and baseline medical/disease condition, baseline SLEDAI 2000 (S2K composite score) and SLE diagnosis. All baseline characteristics summaries will be presented by exposure group (BENLYSTA or NON-BENLYSATA) for the two study cohorts ('Current Users' and 'Treatment Initiators').

Table 1 provides an overview of the planned baseline study population analyses. Details of data displays to be generated are presented in Appendix 11 (Section 9.11.1). Frequency (numbers and percentages) and summary statistics including number of observations, mean, SD, median, range (min; max) and interquartile range (Q1; Q3) will be reported as necessary.

Of note, baseline SLEDAI 2000 descriptive summaries will include:

- Summary statistics of continuous SLEDAI score
- Frequency of each SLEDAI 2000 component (see Section 9.5.5)
- Frequency of SLEDAI 2000 score category and SLEDAI 2000 score grouped (<10 vs.  $\geq 10$ )

